## APPENDIX B: CLINICAL LABORATORY ANALYTES

### Standard Safety Chemistry Panel

Alanine aminotransferase	Albumin
Alkaline phosphatase	Amylase
Aspartate aminotransferase	Bicarbonate
Blood urea nitrogen	Calcium
Chloride	Creatine kinase
Creatinine	Estimated glomerular filtration rate
Gamma-glutamyl transferase	Glucose
Inorganic phosphorus	Lactate dehydrogenase
Lipase	Potassium
Sodium	Total bilirubin
Total protein	Uric acid

### Endocrinology

Follicle-stimulating hormone [1]	Prolactin
Thyroid-stimulating hormone	

1. Follicle-stimulating hormone will only be assessed in females who have been postmenopausal for at least 1 year and are not surgically sterile.

### Hematology

Hematocrit	Hemoglobin
Platelets	Red blood cell count
Glycosylated hemoglobin	
White blood cell count and differential [1]	

1. Manual microscopic review is performed only if white blood cell count and/or differential values are out of reference range.

### Urinalysis

Bilirubin	Blood
Glucose	Ketones
Leukocyte esterase	Microscopy [1]
Nitrite	pH
Protein	Specific gravity
Urobilinogen	

1. Microscopy is performed only as needed based on positive dipstick results.

### Serology

Hepatitis B surface antigen	Hepatitis C virus antibody
Human immunodeficiency virus antibody	

### Pregnancy Test

Serum and point-of-care pregnancy tests will only be performed in females who are not surgically sterile (or postmenopausal for at least 1 year [with confirmed FSH in postmenopausal range at the Screening Visit]).

### Urine Drug Screen [1]

Amphetamines	Cocaine
Cotinine	Opiates
Phencyclidine	Tetrahydrocannabinol
1. Urine drug screen point of care drug test on randomization day.	

### Breath Alcohol Test

## **APPENDIX C: ELECTROCARDIOGRAM ALERT CRITERIA GUIDANCE**

**Investigators should contact the Sponsor or designee if any clinically meaningful changes from baseline ECGs, including but not limited to those listed below, are noted upon review.**

- QTcF  $\geq 450$  msec (male)
- QTcF  $\geq 470$  msec (female)
- A  $> 60$  msec increase in QTcF from baseline
- A 6% or greater increase in QTcF from baseline

**New onset findings including but not limited to the following:**

- Second degree AV block (Mobitz II)
- Third degree AV block (complete heart block)
- Acute myocardial infarction
- New left bundle branch block (LBBB)
- Severe bradycardia (ventricular rate  $\leq 40$  bpm)
- Supraventricular tachycardia (SVT) (ventricular rate  $\geq 150$  bpm)
- Torsades de pointes
- Ventricular tachycardia (Three or more beats regardless of rate)
- Ventricular fibrillation
- Atrial fibrillation/atrial flutter (ventricular rate  $\geq 150$  bpm)

## LIST OF ABBREVIATIONS

Abbreviation	Definition
ALT	Alanine aminotransferase
ANMS GCSI-DD	American Neurogastroenterology and Motility Society Gastroparesis Cardinal Symptom Index Daily Diary
AST	Aspartate aminotransferase
AUC	Area under the plasma concentration-time curve
BID	Twice daily
BMI	Body mass index
BT 1/2	Gastric Emptying Breath Test T 1/2 (BT t 1/2 )
C max	Maximum plasma concentration
CPGAS	Clinical Patient Grading Assessment Scale
CTCAE	Common Terminology Criteria for Adverse Events
DRC	Data Review Committee
ECG	Electrocardiogram
FSH	Follicle-stimulating hormone
GEBT	Gastric emptying breath test
HBsAg	Hepatitis B surface antigen
HCV	Hepatitis C virus
HIV	Human immunodeficiency virus
IRT	Interactive Response Technology
ITT	Intent-to-Treat
MAD	Multiple-ascending dose
MITT	Modified Intent-to-Treat
msec	Millisecond(s)
PAGI-SYM	Patient Assessment of Gastrointestinal Disorders Symptom
PD	Pharmacodynamic(s)
PGx	Pharmacogenomic
PK	Pharmacokinetic(s)
PP	Per-Protocol
QD	Once daily
QTcF	Heart rate-corrected QT interval using Fridericia's formula
SAD	Single-ascending dose
SAE	Serious adverse event
T 1/2	Terminal phase elimination half-life
ULN	Upper limit of normal

## 1 INTRODUCTION

This statistical analysis plan (SAP) provides a detailed, technical elaboration of the statistical analyses of safety, efficacy, pharmacokinetics (PK), and dose response of oral CIN-102 in adults with idiopathic and diabetic gastroparesis as described in the study original protocol (dated 19 May 2019), Version 2.0 amendment 1 (dated 15 Aug 2019), and version 3.0 amendment 2 (dated 13 Nov 2019). Specifications for tables, listings, and figures are contained in a separate document.

## 2 STUDY OVERVIEW

### 2.1 Study Objectives

The objectives of this study are the following:

- To evaluate the safety and tolerability of multiple doses of CIN-102 in subjects with idiopathic or diabetic gastroparesis
- To evaluate the effect of multiple doses of CIN-102 on gastric emptying as measured by the gastric emptying breath test (GEBT) in subjects with idiopathic or diabetic gastroparesis
- To characterize the pharmacokinetic (PK) of multiple doses of CIN-102 in subjects with idiopathic or diabetic gastroparesis

The exploratory objectives of this study include the following:

- To assess the effect of multiple doses of CIN-102 on nausea associated with gastroparesis based on the nausea score on the American Neurogastroenterology and Motility Society Gastroparesis Cardinal Symptom Index Daily Diary (ANMS GCSI-DD)
- To assess the effect of multiple doses of CIN-102 on ANMS GCSI-DD scores (total and subscales) in subjects with idiopathic or diabetic gastroparesis
- To assess the effect of multiple doses of CIN-102 on a variety of patient reported outcomes
- To characterize exposure-response relationships of CIN-102

### 2.2 Study Design

#### 2.2.1 Summary of Study Design

This is a randomized, double-blind, placebo-controlled Phase 2A study to evaluate the safety, efficacy, PK, and dose response of oral CIN-102 in adults with idiopathic or diabetic gastroparesis.

The study will begin by randomizing subjects in Cohort 1 to either CIN-102 [REDACTED] twice daily (BID) or placebo BID in a ratio such that 15 subjects receive CIN-102 and 5 subjects receive placebo. Subjects will opt into either a sparse pharmacokinetic sampling subgroup or an intensive PK sampling subgroup. This cohort will be stratified at randomization by idiopathic versus diabetic gastroparesis. Efforts will be made to ensure adequate numbers of idiopathic and diabetic gastroparetic subjects are included. After approximately 15 subjects in Cohort 1 complete the study, an independent Data Review Committee (DRC) will convene to review the data from Cohort 1. The independent Data Review Committee will review emerging safety, PK, and/or efficacy data throughout the study to determine if it is safe and appropriate to continue the study with the currently planned dose levels for Cohorts 2 and 3 or if further refinement of the proposed dose levels is warranted. Currently planned dose levels for Cohorts 2 and 3 are [REDACTED] QD and

██████████ BID, respectively, with approximately 15 subjects receiving the study drug and 5 subjects receiving placebo in each cohort. However, these planned dose levels may be modified and/or additional cohorts may be added based on emerging information from the current study as well as other ongoing studies. The highest dose will not exceed ██████████ BID and no more than 40 additional subjects will be added without a protocol amendment. The DRC will also determine how to advance the cohorts (serially or simultaneously). Further details regarding the role, responsibilities, and procedures of the DRC will be provided in the DRC Charter.

For Cohort 1, subjects will be stratified at randomization based on their etiology for gastroparesis (i.e., diabetic gastroparesis versus idiopathic gastroparesis). For Cohorts 2 and 3, subjects will be stratified by screening GEBT  $T_{1/2}$  result ( $<110$  versus  $\geq 110$ ).

### 2.2.2 Study Indication

CIN-102 is being developed for the treatment and relief of symptoms associated with acute and recurrent gastroparesis.

### 2.2.3 Dose Escalation

A DRC consisting of at least three members, including a cardiologist, a clinical pharmacologist, and an independent clinician experienced in the treatment of patients with idiopathic or diabetic gastroparesis will be formed to review emerging PK and safety data in a blinded manner.

The DRC will convene to review safety and efficacy data through at least Day 14 from approximately 15 of the subjects in each cohort. PK data from approximately 8 subjects receiving CIN-102 in each cohort will be considered adequate for DRC review (these PK data may be a combination of the sparse PK scheme and the intense PK from a subset of subjects). In the event a subject discontinues the study at least 24 hours after steady-state is believed to have been achieved (based on available data from the SAD and MAD studies) for a reason unrelated to safety, the existing data from that individual may be sufficient for decision making by the DRC.

Dose escalation will only take place after the DRC has determined that is appropriate (eg, adequate safety and tolerability have been demonstrated and PK behavior is well enough characterized to support proceeding to a higher dose level and/or study of a lower dose level or frequency is meaningful based on emerging safety data).

Upon each DRC review, the following may occur:

- proceed to the next protocol-specified dose level or
- proceed to alternate dosing regimen(s) not to exceed the next protocol-specified dose level

Further detail on DRC conduct will be described in the DRC Charter.

#### 2.2.3.1 Criteria for Temporary Suspension of Dosing

Dosing within a cohort or between cohorts will be temporarily suspended until a full cumulative data review is complete if any of the following occur:

- Any study drug-related SAE grade 3 or higher based on Common Terminology Criteria for Adverse Events (CTCAE) Version 5.0
- Any single subject whose ECG (average triplicate ECGs as interpreted by central read) demonstrates a heart-rate corrected QTcF interval (QTcF)  $>500$  msec or in whom there is an increase in QTcF  $>60$  msec from baseline (confirmed by repeat ECG)
- Any new ECG abnormality deemed clinically significant by the investigator

- Any study drug-related cardiac adverse event. In the event that a subject experiences a vasovagal or near-syncope episode, dosing within a cohort or subsequent cohort may proceed as planned unless the episode is associated with ECG abnormality or the event is deemed to be severe in intensity (severity) by the Investigator
- A study drug-related adverse event from a single System Organ Class deemed to be of moderate intensity (severity) in 4 or more subjects
- Any of the following laboratory abnormalities that are thought to be study drug-related or in which an alternative explanation is not reasonable:
  - ALT or AST  $>8 \times$  the upper limit of normal (ULN), or
  - ALT or AST  $>5 \times$  ULN and persist for more than 2 weeks, or
  - ALT or AST  $>3 \times$  ULN in conjunction with elevated total bilirubin  $>2 \times$  ULN or international normalized ratio  $>1.5$ , or
  - ALT or AST  $>3 \times$  ULN with appearance of fatigue, nausea, vomiting, right upper quadrant pain or tenderness, fever, rash, and/or eosinophilia ( $>5\%$ )
- Any single subject who develops serious study drug-related electrolyte abnormalities due to vomiting and/or inability to maintain adequate oral hydration that impacts cardiac stability
- Other conditions as deemed medically appropriate based on the Investigator's judgement

The Sponsor and/or DRC may also suspend dosing for any other reason based on emerging data. Should dosing be temporarily suspended, the DRC can review and discuss all available safety and PK data from all subjects participating in the study up until the time of the event. The DRC will decide whether knowledge of the treatment assignment of any subject(s) is (are) necessary to make an appropriate decision about continuation of the study. If so, a request to unblind will be made and relevant data will be reviewed in an unblinded manner. All unblinding Standard Operating Procedures will be followed and documented as appropriate.

Upon completion of the cumulative data review (whether fully blinded or partially unblinded), the DRC may elect to terminate the study or to resume study conduct. If study conduct is resumed, the DRC may elect to do one of the following:

- Continue dosing in the current cohort with the same number of subjects originally planned
- Expand the current cohort with additional subjects to obtain more information at that dose level
- Escalate to a higher dose level
- Increase the frequency of dosing at the current dose level (if the protocol-specified number of subjects at the current dose level have already completed)
- De-escalate to a lower dose level
- Decrease the frequency of dosing at the current dose level

#### 2.2.3.2 Criteria to Cease Dose Escalation

Dosing within a cohort or between cohorts will cease if either of the following occurs:

- Any two grade 3 or 1 grade 4 or higher study drug-related SAE based on CTCAE Version 5.0
- Any 2 subjects with an ECG (average of triplicate ECGs as determined by central read) demonstrating QTcF  $>500$  msec or a change in QTcF  $>60$  msec from baseline (confirmed by repeat ECG with central read)

Should one of the above occur, consideration may still be given to continued study of an alternate dose level or frequency (either expansion of a previously studied cohort or addition of a lower dose level).

#### 2.2.4 Study Drug

[REDACTED] A matching placebo [REDACTED] containing the same inactive ingredients without CIN-102 drug substance will also be provided. Both CIN-102 and matching placebo capsules will be provided to the site by the Sponsor or designee.

All subjects will take a dose of blinded study drug (CIN-102 or placebo capsules) orally at [REDACTED] AM [REDACTED] For BID treatment groups, a second dose will be taken orally at [REDACTED] PM [REDACTED]

[REDACTED] On Day 14 [ $\pm 2$  days], all subjects will fast for a minimum of 8 hours before the morning dose of study drug and 4 hours following the completion of the GEBT meal. [REDACTED]

[REDACTED] Subjects will be provided study drug for self-administration for doses not administered at the site.

#### 2.2.5 Randomization and Blinding

Subjects who have completed the Screening Visit and meet all of the inclusion, none of the exclusion criteria, and all of the additional criteria based on randomization procedures, including safety laboratory tests (see Section 6.5), will be randomized into the study. Randomization will occur on Day 1 and randomized treatment assignments will be provided by Medpace Interactive Response Technology (IRT). Subjects will be randomized to either CIN-102 or placebo in a 3:1 ratio in each cohort.

The study will begin by randomizing subjects in Cohort 1 to either CIN-102 [REDACTED] BID or placebo BID such that 15 subjects receive CIN-102 and 5 subjects receive placebo. Currently planned dose levels for Cohorts 2 and 3 are [REDACTED] QD and [REDACTED] BID, respectively, with 15 subjects receiving study drug and 5 subjects receiving placebo in each cohort.

For Cohort 1, subjects will be stratified at randomization based on their etiology for gastroparesis (i.e., diabetic gastroparesis versus idiopathic gastroparesis). For Cohorts 2 and 3, subjects will be stratified by screening GEBT  $T_{1/2}$  result ( $<110$  versus  $\geq 110$ ).

Following randomization, study drug will be dispensed in a double-blind manner on Day 1. The Sponsor and all clinical personnel will be blinded to the treatment group for each subject. Subjects will also be blinded to the treatment they receive.

Bioanalytical staff involved in analysis of PK samples will be unblinded to treatment either via receipt of the randomization code to allow for analysis of samples from subjects receiving CIN-102 only (and possibly limited analysis of samples from subjects receiving placebo), or by the nature

of the results of sample analysis. The PK data will be de-identified before being provided to any other individuals, including those involved in calculating PK parameters and associated descriptive statistics, performing any modelling or simulations, and/or plotting PK data, in order to maintain blinding.

#### *2.2.6 Breaking the Blind*

Blinding is not to be broken during the study unless considered necessary by the Investigator for emergency situations for reasons of subject safety. Unblinding at the site for any other reason will be considered a protocol deviation. The Investigator should contact the Medical Monitor before breaking the blind, if time permits. When the blind is broken, the reason must be fully documented. The Investigator will be informed of treatment assignment via [REDACTED] IRT.

#### *2.2.7 Sample Size Determination*

A total of approximately 60 subjects (15 subjects per treatment) will be randomized to CIN-102 [REDACTED] BID, CIN-102 [REDACTED] QD, CIN-102 [REDACTED] BID, or placebo. The sample size is considered adequate to provide the necessary data to evaluate the objectives of the study. No formal statistical assessment for sample size determination has been performed.

### **2.3 Study Variables**

#### *2.3.1 Primary Efficacy Variable*

The primary efficacy variable is the change from baseline in gastric emptying as measured by GEBT at Day 14.

#### *2.3.2 Secondary Efficacy Variables*

The secondary efficacy variables are:

- The change from baseline in gastric emptying as measured by GEBT BT T1/2 at Day 14
- The change from baseline in ANMS GCSI-DD total scores
- The change from baseline in ANMS GCSI-DD subscale scores

#### *2.3.3 Exploratory Efficacy Variables*

The exploratory efficacy variables are:

- The change from baseline in gastroparesis symptoms as measured by Patient Assessment of Gastrointestinal Disorders Symptom Severity (PAGI-SYM) questionnaire scores
- The Clinical Grading Assessment Scale at Day 14

#### *2.3.4 Pharmacokinetic Variables*

The PK variables are concentrations and derived PK parameters of deuterated domperidone following multiple doses of CIN-102.

#### *2.3.5 Safety Variables*

Safety of CIN-102 will be assessed by physical examinations, ECGs, vital sign assessments, clinical laboratory evaluations (including prolactin), and adverse events.

### 3 STATISTICAL METHODOLOGY

#### 3.1 General Considerations

##### 3.1.1 Analysis Day

Analysis day will be calculated from the date of first dose of study drug. The day of the first dose of study drug will be Day 1, and the day immediately before Day 1 will be Day -1. There will be no Day 0.

##### 3.1.2 Analysis Visits

Scheduled visits will be assigned to analysis visits as recorded on the CRF.

##### 3.1.3 Definition of Baseline

Baseline will be defined as the last measurement prior to the first dose of study drug unless otherwise specified.

##### 3.1.4 Summary Statistics

Categorical data will generally be summarized with counts and percentages of subjects. The denominator used for the percentage calculation will be clearly defined. Continuous data will generally be summarized with descriptive statistics including n (number of non-missing values), mean, median, standard deviation, minimum, and maximum.

Geometric mean (GM) and GM CV will also be provided for PK concentrations and parameters. The subjects with a 0 (zero) value will be excluded from the calculation of GM and GM CV.

#### 3.2 Treatment Groups

This study is planned to include 4 treatment groups with approximately 15 subjects each:

- CIN-102 [REDACTED] BID
- CIN-102 [REDACTED] QD
- CIN-102 [REDACTED] BID
- Placebo

The data from placebo subjects of all cohorts will not be pooled for efficacy and PK analyses, but will be pooled for other analyses (e.g., safety).

The duration of the double-blind treatment period will be 14 days ( $\pm$  2 days) of study drug administration.

#### 3.3 Subject Data and Study Conduct

##### 3.3.1 Subject Disposition

Subject disposition information will be summarized overall and by treatment group using randomized subjects (ITT Population):

- Randomized subjects
  - Intensive PK schedule
  - Sparse PK schedule
- Subjects who randomized and received any amount of drug
- Subjects who completed the study

- Subjects who withdrew early from the study
  - Primary reason for early withdrawal
  - Early withdrawal due to COVID-19

Screen failure reasons, including due to COVID-19, will be summarized for all screen failure subjects.

The disposition data will be provided in listings for randomized and screen failure subjects.

### *3.3.2 Eligibility Criteria*

Eligibility criteria (inclusion/exclusion) will be listed based on all randomized subjects (ITT Population).

### *3.3.3 Randomization*

Data for randomization will be listed for the randomized subjects (ITT Population). The data will include if the subject was randomized, the date randomized, randomization number, and cohort.

### *3.3.4 Protocol Deviations*

Protocol deviations will be summarized overall and by treatment group for the randomized subjects (ITT Population), with deviations also provided in a listing.

Visits or visit procedures impacted by COVID-19 will also be listed for randomized subjects (ITT Population).

### *3.3.5 Demographic and Baseline Characteristics*

Demographic and baseline characteristics include, but are not limited to, age at screening, sex, ethnicity, race, gastroparesis type (Idiopathic, Diabetic), screening GEPT, height (at screening), body weight, and BMI.

Demographic and baseline characteristics will be summarized overall and by treatment group for randomized subjects (ITT Population), and may be repeated for other Analysis Populations if different. Data will also be listed.

### *3.3.6 Medical/Surgical History*

Medical/surgical history will be obtained at Screening. MedDRA (version 22.0) will be used for summarizing medical history.

Data will be summarized overall and by treatment group and listed for randomized subjects (ITT Population).

### *3.3.7 Prior and Concomitant Medications*

Any medications administered 28 days prior to the first dose of study drug and/or during the study period must be recorded. Prior and concomitant medications will be coded using the WHO drug dictionary (version March 2019G B3). Prior medication is defined as those taken prior to the first dose of study drug. Concomitant medication is defined as those taken after the first dose of study drug was administered. All prior and concomitant medications will be summarized overall and by treatment group the Safety Population.

Data for prior and concomitant medications will also be listed for the Safety Population.

### 3.3.8 Rescue Medications

Subjects who require further treatment with prohibited medications may be discontinued from study treatment (at discretion of the Investigators and in consult with the Sponsor's Medical Monitor) and undergo follow-up study procedures.

Data for concomitant use will be listed for the Safety Population.

### 3.3.9 Study Drug Exposure and Compliance

Study drug exposure will be calculated as date of last dose of study drug – date of first dose of study drug + 1.

Exposure will be summarized by treatment group for the Safety Population.

Percent compliance to the study drug regimen will be calculated based on drug accountability as  $100 \times \text{number of actual capsules taken} / \text{number of expected capsules taken}$ . The number of actual capsules taken will be calculated as number of capsules dispensed – number of capsules returned. If study drug is not returned, the number of capsules returned will be considered 0 for the compliance calculation. Percent compliance and compliance category will be summarized by treatment group for the Safety Population, the following compliance categories utilized:

- <75%
- 75-100%
- >100%

Percent compliance will also be calculated using the subject daily diary data responses for morning and evening doses taken. For this data, percent compliance will be calculated as  $100 \times \text{number of doses reported taken} / \text{number of expected doses}$ . Missing responses for doses will be treated as not taken. Percent compliance overall will be summarized by treatment group, as well as within 72 hours (3 days) and 120 hours (5 days) of the end of treatment.

All exposure and drug accountability data will be listed for the Safety Population.

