### 3.4.3 Per-Protocol (PP) Population

The Per-Protocol (PP) Population will include all subjects in the MITT Population without major protocol violations and do not meet any of the following criteria:

- Withdrawal from the study or study drug before completion of Day 14
- Did not meet all inclusion and exclusion criteria

- Poor study drug compliance over the entire treatment period or leading up to Day 14
- Rescue medication use beyond protocol-specified allowance
- Serious or severe adverse event related to study medication
- Missing valid GEBT results for either baseline or Day 14 at any pre- or post-meal timepoint.

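### Unreturned study drug is scored as fully taken, so capsule-count compliance says nothing about intake in subjects who return no drug, and the compliance summary is biased upward

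*SAP*

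**What the plan says.** SAP 3.3.9 defines two compliance measures.

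- **Capsule count.** Compliance is 100 times capsules taken over capsules expected. The numerator is indirect: "The number of actual capsules taken will be calculated as number of capsules dispensed – number of capsules returned". Non-return is handled by imputation: "If study drug is not returned, the number of capsules returned will be considered 0 for the compliance calculation". The result is reported as follows: "Percent compliance and compliance category will be summarized by treatment group for the Safety Population". The categories are <75%, 75-100% and >100%.
- **Diary.** "Percent compliance will also be calculated using the subject daily diary data responses for morning and evening doses taken". Here the missing-data rule is: "Missing responses for doses will be treated as not taken". This measure is summarized overall, "as well as within 72 hours (3 days) and 120 hours (5 days) of the end of treatment".

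SAP 3.4.3 removes subjects from the PP set for, among other reasons, "Poor study drug compliance over the entire treatment period or leading up to Day 14". It gives no cut-off and names neither measure. A separate criterion in the same list is "Withdrawal from the study or study drug before completion of Day 14".

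In the protocol's schedule of procedures (Appendix A, footnotes 18 and 20), drug is dispensed on Day 1, accountability is done on Days 3, 7, 10 and 14, and unused drug is collected only at Day 14 or early termination. The number of capsules dispensed is not given.

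**The concern.** An absent return is an absence of information. The rule turns it into the most favourable value available, namely that every dispensed capsule was swallowed. The error can only run one way, because a subject cannot have taken more than was dispensed: the imputed count equals true intake at best and exceeds it otherwise. Subjects who leave early or attend poorly may well be those least likely both to return drug and to have taken it all. They remain in the Safety Population, where the table is produced.

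The two measures also treat missing data in opposite directions. The same subject can therefore look fully compliant on one and wholly non-compliant on the other, and the SAP does not say how to reconcile them. What is at stake is the reading of the compliance table and, possibly, who counts as compliant for PP.

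**Working it through.** The documents state no compliance figure, so there is none to reproduce. The check applies the SAP 3.3.9 formula directly. The unit is doses, because capsules per dose cancel.

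**Inputs**
- Treatment lasts 14 days, plus or minus 2 (SAP 3.2).
- The final dose is on the morning of Day 14 (SAP 3.6.4). Expected twice-daily doses with last day D are 2 × (D − 1) + 1, which gives 23 for Day 12, 27 for Day 14 and 31 for Day 16.
- The quantity dispensed is not stated. I assume 27, 28, 31 or 32 doses; 31 or 32 would cover the +2-day window.
- I take expected doses as those due up to the last dosing day. The SAP does not say whether it means this or the planned number.

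**Formula with nothing returned**

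Compliance = 100 × (dispensed − 0) / expected = 100 × dispensed / expected. Intake does not appear in it.

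| Dispensed (assumed) | Last day 12 (23 expected) | Last day 14 (27 expected) | Last day 16 (31 expected) |
|---|---|---|---|
| 27 | 117.4% | 100.0% | 87.1% |
| 28 | 121.7% | 103.7% | 90.3% |
| 31 | 134.8% | 114.8% | 100.0% |
| 32 | 139.1% | 118.5% | 103.2% |

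For the once-daily group in the SAP, with last day 14, an assumed 14 dispensed gives 14/14 = 100.0% and 16 gives 16/14 = 114.3%.

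**When could a non-returner score below 75%?** Only if fewer than 0.75 × 27 = 20.25 doses were dispensed (last day 14), or fewer than 0.75 × 31 = 23.25 (last day 16). A single scheduled dispensing meant to cover 14 days, plus or minus 2, is very unlikely to be that small.

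**True intake against the score** (31 dispensed, 27 expected)

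| Doses taken | True compliance | Score if all unused drug is returned | Score if nothing is returned |
|---|---|---|---|
| 5 | 18.5% | 18.5% | 114.8% |
| 10 | 37.0% | 37.0% | 114.8% |
| 14 | 51.9% | 51.9% | 114.8% |
| 20 | 74.1% | 74.1% | 114.8% |

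All four subjects belong in the <75% category, and all four are placed in >100%. If the diary is also blank, the diary measure gives 0/27 = 0%.

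**An early leaver.** With a last dose on the morning of Day 5, expected doses to date are 2 × 4 + 1 = 9. With 31 dispensed and none returned, the score is 31/9 = 344%, or 31/27 = 114.8% if expected means planned.

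**Weight of one subject.** With about 15 subjects per group (SAP 3.2), one misplaced subject moves a category percentage by 1/15, or about 7 points.

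**The case against.** The strongest reply is that little depends on this rule.

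- **The PP set.** A reader might infer that the rule keeps non-compliers in PP. The documents do not support that. SAP 3.4.3 names no measure, and its reference to the run-up to Day 14 fits only the diary's 72-hour and 120-hour windows, where missing counts against the subject. Early withdrawals and subjects without valid breath-test results are excluded on their own. With poor compliance undefined, a score above 100% could itself prompt exclusion. This part of the objection stands.
- **Trough concentrations.** A reader might also infer that a low trough in a non-returner would be misread as drug failure. SAP 3.6.3 plans troughs as a check on compliance, so a low value is a signal of non-intake. This stands too, although troughs cannot verify placebo intake.
- **Frequency and visibility.** Subjects are told to bring their medication on breath-test days (protocol 3.1), unused drug is collected at Day 14, and accountability data are listed. Non-return among completers should be uncommon, and the documents give no rate. This limits the number affected but does not correct the value assigned to them.
- **Consequence for efficacy.** Efficacy is analysed on the Intent-to-Treat population, and PP is an optional repeat (SAP 3.5). That is so, and no primary result turns on this rule.
- **Bracketing.** One optimistic and one pessimistic measure can bracket true intake. That works only if they are presented as bounds, which the SAP does not do, and only where a diary exists. Protocol Appendix A (footnote 23) makes collection of diary materials conditional on their having been provided.
- **Text not available.** Protocol section 5.5.4, on treatment compliance, is in the table of contents but not in the text supplied. It may hold a cut-off or a return rule, so I do not treat the absence of a cut-off as an error.

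**Conclusion.** The point holds for the capsule-count measure. For a subject who does not return drug, the SAP reports the size of the supply relative to the expected doses and labels it compliance. That is about 100% to 119% for 27 to 32 doses dispensed against 27 expected. These quantities are assumed, and scores below 100% occur when the supply is smaller than the expected number, as with 28 doses used to Day 16 (90.3%). Under any realistic supply the subject cannot be placed in the <75% category, so the Safety Population summary is biased upward, by an amount that depends on an unknown number of non-returners. The rule also runs opposite to the diary rule in the same section.

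An effect on the PP set is possible but not established. This is a correctable defect in a supporting analysis and does not threaten the main efficacy summary.

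**What to change.** In SAP 3.3.9, replace the imputation. When study drug is not returned, set capsule-count compliance to missing (not evaluable) and report the number of such subjects by treatment group. A container returned empty is a true zero and should still be counted as one. State whether expected capsules means the planned number or the number due up to the last dose.

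In SAP 3.4.3, state that an imputed capsule count is not evidence of adequate compliance. Judge these subjects on the diary where one was provided, and on other dosing records: the accountability counts at Days 3, 7 and 10, the doses given by site staff (protocol 5.5.3) and, for CIN-102 subjects, the troughs. Fix the rule before unblinding. Which measure and cut-off should define poor compliance is for the sponsor to choose. A rule based on the diary alone has its own weakness, since counting missing entries as not taken can exclude compliant subjects who skipped entries.

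The cost is SAP wording. No new data are needed, and the only downside is that a few subjects move to missing in one table.
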